11.2 Amendments to the protocol

The amendment procedure will be pertinent when there is a need to make any change to a document that is part of the research project or protocol, derived from variations in the methodological structure, substitution of the principal investigator or in the face of the identification of risks in the research subjects. The documents that may be amended will be: protocol, form of informed consent, researcher's manual, documents for the subject, measurement scales and schedule of activities.

Any amendment must be approved by the sponsor and/or the principal investigator, the amended document(s), once reviewed and approved by the CEI and the IC or, when applicable, by the Biosafety Committee, (entities that issued the initial favorable opinion for the conduct of the research) will be sent for authorization by COFEPRIS.

Amendments that substantially modify the protocol confer an additional or different risk on the research subjects must be approved by the aforementioned Committees. It is the investigator's responsibility to take action in situations that require immediate action to avoid unnecessary harm to study participants.

The principal investigator is responsible for communicating to the Research Ethics Committee any amendments to the protocol that may eventually affect the rights, safety, or welfare of research participants. Likewise, it must inform of any situation or new knowledge that will show a greater risk for the participants, the premature termination or suspension of the study, the reasons and the results obtained so far. It must also report on the conclusion of the study, upon completion of the research protocol.

11.3 Early Study Termination

The study may be temporarily suspended or terminated prematurely if there is a sufficiently reasonable cause. Written notice, documenting the reason for the suspension or early termination, must be delivered by the party executing the suspension. The PI should promptly inform the study participants, the IC, and the IRC providing the reasons.

Situations in which study suspension or early termination will be contemplated include, but are not limited to:

1. The presence of serious adverse events in more than 10% of participants in a study group.
2. The regulatory authority (COFEPRIS) considers it for security alerts.
3. The Sponsor determines it for its convenience or eventualities such as: financial support, manufacturing errors, etc.
4. The identification of unexpected risks to the participants, which are significant or unacceptable.
5. Obtaining new relevant safety information.
6. Insufficient adherence to the requirements of the protocol.
7. The data obtained are not assessable or are not sufficiently complete.
8. The determination that the primary objective has been achieved.

9. The determination of futility.

In the event of suspension, the study may be resumed once the situations that led to the suspension have been corrected; as long as this justification is sufficient for the sponsor, CI, CEI and regulatory authorities.

11.4 Informed Consent

The FCI contains complete and understandable information about the study and the investigational product, in accordance with the applicable regulations in force and Good Clinical Practice.

The FCI will be considered as a source document and will be filed as such. The site's principal investigator is responsible for ensuring that all new versions of the informed consent are submitted to the appropriate approvals (the same as those to which the original informed consent form was submitted) and that the most current approved version is the one presented to the study subjects.

11.4.1 Obtaining

Informed consent must be obtained before the subject undergoes any procedure indicated in the protocol. For this purpose, the informed consent form must be signed.

Written consent documents will incorporate the elements of informed consent described in the Declaration of Helsinki and the ICH Guide to Good Clinical Practice and will be in compliance with all applicable laws and regulations.

The PI, or the study staff delegated by him/her, will provide the prospective participant with all the information regarding the characteristics of the study, its potential benefits, risks, objectives, and procedures.

This information will be in a language understandable to the subject, it will be explained to the subject that he or she has the right to interrupt his or her participation in the study at any stage, without this affecting the relationship with the researcher and/or his or her future assistance. Informed consent will be put to the consideration of the potential participant; He must have enough time to analyze each and every one of the aspects mentioned above and in case he has any doubts, it will be clarified by the person in charge of obtaining the informed consent.

Once the participant agrees to participate in the study, he/she must sign and date the informed consent form in the presence of two witnesses who are or are not related to the study subject, who will participate during the informed consent process and will sign guaranteeing that the process was carried out prior to any study procedure. that the information of the study was clearly explained and doubts were clarified if any.

In the event that a subject is illiterate, acceptance will be with his or her fingerprint, and in the event that the subject is unable to give adequate written informed consent, a representative of the "legally

"authorized" subject may provide such consent for the subject in compliance with applicable laws and regulations.

In the same way, the PI, or the study staff delegated by him, must sign and date this consent.

The FCI must be signed in duplicate by all those involved, one copy will be filed in the researcher's folder and the other will be given to the participant. The PI or delegated personnel must document the process of obtaining the Informed Consent by means of a detailed, precise and contemporary medical note, specifying the signed version, the date on which the document was signed and how the process was carried out.

11.4.2 Special considerations

The procedures that will be performed during the conduct of the study do not pose an additional risk that should be considered apart from the procedures listed for informed consent.

11.4.3 Modifications to informed consent

Any changes to the FCI constitute an amendment to this document and must be submitted for approval to the Research, Research Ethics and COFEPRIS Committees.

Such amendments may be implemented only after obtaining the written approval of the Research Ethics Committee and authorization from COFEPRIS (as applicable), except for an amendment that is required to eliminate an immediate danger to study subjects.

A process of re-consent of each subject affected by the amendment must be carried out under the same conditions as those described above, in order to communicate the new information contained in the document to them in a timely manner. The subject will be given a signed original of the amendment and the researcher will keep the second original.

11.5 Confidentiality

All documents and information provided to the research center by the sponsor are strictly confidential. PI expressly agrees that data about your professional and clinical experience, provided to the sponsor on paper and stored in electronic form, is solely for use related to your activities with the clinical trial sponsor, in accordance with Good Clinical Practice.

The PI agrees that he and his team members will use the information only within the framework of this study, to carry out the protocol. This agreement is binding as long as the confidential information has not been disclosed to the public by the sponsor.

The clinical study protocol provided to the PI may be used by the PI and his team to obtain the informed consent of the subjects for the study. The clinical trial protocol, as well as any information taken from it, should not be disclosed to other parties without the written permission of the sponsor.

The PI will not disclose any information without the prior written consent of Laboratorios Sophia, S.A. de C.V., except to the representatives of the Competent Authorities, and only at their request. In the

latter case, the investigator undertakes to inform Laboratorios Sophia, S.A. de C.V. before disclosing the information to these authorities.

The PI will fill out and maintain a record of the selection of the subjects, as well as the identification and enrollment list of each of the subjects participating in the study. The investigator agrees to give on-site access to the auditor and/or representatives of the Competent Authorities. The information will be processed in compliance with professional secrecy.

In the eCRF and all communications related to study subjects, they will identify them only by the study subject's identification number, either by the scrutiny number or the assignment number. The information collected in this study will be exchanged between the sponsor and the research center, and must be treated confidentially. The Health Authority, the CEI, the IC, the sponsor, the monitors/auditors and third-party auditors will be the only bodies authorized to review the study documentation. If publications arise from this research project, in no case will they contain information on the identification of the study subjects. If the results of the study are published, no personal information of the study subjects will be revealed.

The protection of personal data will be carried out in accordance with the corresponding regulations in force.

11.6 Conflict of interest

The independence of the conduct of the study and its results from any current or perceived external influences is critical. For this reason, any current conflict of interest of any person who has a role in the design, conduct, analysis, publication or any aspect of this study will be declared. Furthermore, those who have a perceived conflict of interest will be asked to handle it in a manner appropriate to their participation in the study.

11.6.1 Declaration of Interests

The PI undertakes to make a declaration of financial interests as well as conflict of interest prior to the start of the study.

11.7 Access to Information

The final database of the study will be the property of Laboratorios Sophia, S.A. de C.V. and its access will be restricted. The PI will not have access to it, unless it has prior written authorization from the sponsor.

The information obtained, which is relevant to the safety of the subjects participating in the study, must be immediately shared with the research center, so that it can be notified to the study subjects.

11.8 Ancillary and post-study care

Upon completion of the study and closure of adverse events in accordance with section: 8, the sponsor shall not extend care to the research subject.

12. Biosecurity aspects

NO BIOSECURITY IMPLICATIONS

This protocol, entitled: "Phase I clinical study, to evaluate the safety and tolerability of the ophthalmic solution PRO-231, versus VIGAMOXI,® on the ocular surface of ophthalmologically and clinically healthy subjects", and number: SOPH231-1221/I has no biosafety implications, since infectious-contagious biological material; pathogenic strains of bacteria or parasites; viruses of any type; radioactive material of any type; animals and/or cells will NOT be used and/or genetically modified plants; toxic, dangerous or explosive substances; any other material that endangers the health or physical integrity of the research centre's staff or research subjects or affects the environment. It is also declared that this project will not carry out cell, tissue or organ transplant procedures, or cell therapy, nor will laboratory, farm or wildlife animals be used.

13. Posting Policy

13.1 Final Report

Once the statistical analysis is completed, the final report will be written with the results obtained, by the Team of the Regional Management Department of Medical Affairs of Laboratorios Sophia, S.A. de C.V. This report will be prepared following the recommendations of the *E3 Step 4 Guide* of the ICH.

13.2 Communication of results

Regardless of the results of the study, Laboratorios Sophia, S.A. de C.V., is committed to communicating the final report of the study to the principal investigators and COFEPRIS. These results will also be shared with the IC and the IEC. It will be the responsibility of the PI to communicate it to the research subjects.

Laboratorios Sophia, S.A. de C.V. will maintain at all times the rights over the publication and disclosure of the information contained.

13.3 Publication of results

Laboratorios Sophia, S.A. de C.V., acting as the sponsor of the study, assumes full responsibility for its function and retains exclusive ownership rights over the results of the study, which it may use in any way it deems appropriate.

The PI undertakes not to publish or communicate data collected from the study, unless there is the prior written agreement of Laboratorios Sophia, S.A. de C.V. Any manuscript derived from the data obtained with this protocol must be submitted to review by the sponsor before any attempt to submit it for publication in any scientific journal or congress.

However, in the event that the sponsor is in the process of filing a patent application on the results of the study, the sponsor may delay its publication or communication of the results of the study until the date of registration or whenever it deems appropriate.

The assignment of authorship of publications, which is the responsibility of the sponsor, will be the prerogative of the latter. However, the express authorization of the people who are invited to participate as authors must be obtained. Authors have the right to review the manuscript prior to its publication, as well as to issue comments and suggestions in this regard, such comments must be delivered within the first 15 calendar days from the date on which the project is received.

14. Financing and Insurance

14.1 Compensation to Study Participants

Subjects who participate in the study will not receive financial compensation for their participation in the study. However, the subjects will receive financial support for travel expenses in each scheduled visit to which they attend punctually. Such support, as well as the amount, may be specified in the form of informed consent.

16.1 Cartilla de Snellen

Cartilla de Snellen. Taken from Azzam and Ronquillo, 2021 [65]

The above annex is a representation of the Snellen booklet, it is possible that the booklet designated for the study has variations in format.

16.2. Efron Scale for Conjunctival Hyperemia

16.3 Oxford scale

Panel	Staining pattern	Degree	Criterion	Verbal Description
A		0	Equal to or less than panel A	Absent
B		I	Equal to or less than panel B, greater than panel A	Minimum
C		II	Equal to or less than panel C, greater than panel B	Lightweight
D		III	Equal to or less than panel D, greater than C	Moderate
And		IV	Equal to or less than panel E, greater than panel D	Marked
>E		V	Larger than panel E	Severe

Oxford scale. Staining is represented by the dotted pattern (adapted from Bron AJ et al, 2003) [42]

16.4 Eye Comfort Index (JI)

Índice de Confort Ocular

Ficha de Identificación

No. de estudio: SOPH231-1221/I

Fecha: _____

Iniciales del sujeto: _____

No. de sujeto: _____

Indicaciones:

Este cuestionario fue diseñado para calificar el confort de sus ojos.

Para cada pregunta circule su respuesta

Ejemplo: En la semana pasada, ¿qué tan seguido sus ojos estuvieron rojos?

Nunca	0	1	2	3	4	5	Siempre	6
--------------	---	---	---	---	---	---	----------------	---

No existen respuestas correctas o incorrectas. No tome demasiado tiempo en cada pregunta.

1 En la semana pasada, ¿qué tan seguido sus ojos se sintieron secos?

Nunca	0	1	2	3	4	5	Siempre	6
--------------	---	---	---	---	---	---	----------------	---

Cuando sus ojos se sentían secos, por lo general, ¿qué tan intensa era la sensación?

No he sentido	0	1	2	3	4	5	Severo	6
----------------------	---	---	---	---	---	---	---------------	---

2 En la semana pasada, ¿qué tan seguido sus ojos se sintieron arenosos?

Nunca	0	1	2	3	4	5	Siempre	6
--------------	---	---	---	---	---	---	----------------	---

Cuando sus ojos se sentían arenosos, por lo general, ¿qué tan intensa era la sensación?

No he sentido	0	1	2	3	4	5	Severo	6
----------------------	---	---	---	---	---	---	---------------	---

3 En la semana pasada, ¿qué tan seguido sus ojos sintieron punzadas?

Nunca	0	1	2	3	4	5	Siempre	6
--------------	---	---	---	---	---	---	----------------	---

Cuando sus ojos sentían punzadas, por lo general, ¿qué tan intensa era la sensación?

No he sentido	0	1	2	3	4	5	Severo	6
----------------------	---	---	---	---	---	---	---------------	---

4 En la semana pasada, ¿qué tan seguido sus ojos se sintieron cansados?

Nunca	0	1	2	3	4	5	Siempre	6
--------------	---	---	---	---	---	---	----------------	---

Cuando sus ojos se sentían cansados, por lo general, ¿qué tan intensa era la sensación?

No he sentido	0	1	2	3	4	5	Severo	6
----------------------	---	---	---	---	---	---	---------------	---

Hoja 1 de 2

Índice de confort ocular

5 En la semana pasada, ¿qué tan seguido sus ojos se sintieron *adoloridos*?

Nunca

0

1

2

3

4

5

SiempreSevero

6

No he sentido

0

1

2

3

4

5

6

6 En la semana pasada, ¿qué tan seguido sus ojos sintieron *comezón*?

Nunca

0

1

2

3

4

5

SiempreSevero

6

No he sentido

0

1

2

3

4

5

6

Cuando sus ojos sentían *comezón*, por lo general, ¿qué tan intensa era la sensación?

Índice de confort ocular, traducido del Ocular Comfort Index disponible en: <http://iovs.arvojournals.org>

Hoja 2 de 2

16.5 Fraction to LogMAR conversion table.

LogMAR Value	Snellen (pies)	Snellen (metros)
1.6	20/800	20/240
1.5	20/640	6/190
1.4	20/500	6/150
1.3	20/400	6/120
1.2	20/320	6/96
1.1	20/250	6/75
1.0	20/200	6/60
0.9	20/160	6/48
0.8	20/125	6/38
0.7	20/100	6/30
0.6	20/80	6/24
0.5	20/63	6/19
0.4	20/50	6/15
0.3	20/40	6/12
0.2	20/32	6/9.5
0.1	20/25	6/7.5
0.0	20/20	6/6
-0.1	20/15	6/4.5
-0.2	20/12	6/3.6

Visual acuity equivalence table (adapted from *Ophthalmic & Physiological Optics*, 2016) [69]

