6.1.2 Investigational Product Dosage

Dosage: 1 drop three times a day (DID) for 7 days, in the right eye (OD).

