6.1.5 Comparator Product Dosage

Dosage: 1 drop TID for 7 days, in OD.

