7.4.1.2 Tolerability

- ICO score changes.

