7.4.4 Description of the variables, methods and scales for their measurement

For clinical purposes, ophthalmological evaluations will be carried out in both eyes, and their record will be recorded in the clinical file. However, in order to obtain results and comply with the assumption of independence within the variables, only the examinations and qualifications of the right eye will be recorded in the eCRF when appropriate. Next, the description of the variables is made, which are not in order of execution.

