7.4.4.3 Ocular symptomatology

The subject will be questioned directly about the presence in general (since the last visit) of the following symptoms: burning, foreign body sensation, pruritus, tearing.

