10.1.2 Size Calculation

PRO-231 ophthalmic solution is expected to be safe in its ophthalmic application as it presents an incidence of AE similar to that presented by VIGAMOXI.®

On this basis, a sample of 17 ophthalmologically and clinically healthy subjects was estimated. This value increased by 10% considering possible losses. Based on this consideration, 19 subjects per arm (38 subjects in total) are required to provide one eye (OD) to respond to the primary objective of the study.

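### Only the right eye is treated, but the ICO asks about both eyes and the symptom questions name no eye, so complaints from the untreated eye can enter both tolerability outcomes

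*Combined protocol and SAP*

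**What the plan says.** **Treatment.** Sections 6.1.2 and 6.1.5 put both products in the right eye only; for the comparator, "Dosage: 1 drop TID for 7 days, in OD".

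**Unit of analysis.** Section 10.1.2 states that the subjects "are required to provide one eye (OD) to respond to the primary objective of the study". Section 7.4.4 has both eyes examined for clinical purposes but, for independence, "only the examinations and qualifications of the right eye will be recorded in the eCRF when appropriate".

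**ICO.** Section 7.4.1.2 lists one primary tolerability variable, "ICO score changes". The form in annex 16.4 introduces itself with "Este cuestionario fue diseñado para calificar el confort de sus ojos", and its items follow the pattern "En la semana pasada, ¿qué tan seguido sus ojos se sintieron secos". Every item legible in the annex uses the plural *sus ojos* and asks about the past week. Neither the form, section 7.4.4.7, Table 2 (section 7.4.3) nor the visit lists in 7.7 tell the subject to answer for the treated eye. Section 7.4.4.7 lets the evaluator help only when a question is not understood.

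**Symptoms.** Section 7.4.4.3 reads "The subject will be questioned directly about the presence in general (since the last visit) of the following symptoms". Each answer is a single present or absent. Table 2 refers to the general presence of symptoms. Neither place names an eye.

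**Decision rule.** The table in section 10.3.1 reads a p-value of at least 0.05, with a 95% CI that includes zero, as the two treatments being similar in safety and tolerability.

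**The concern.** The examined outcomes (hyperemia, visual acuity, staining) are described eye by eye, so the right-eye result can be isolated. The two self-reported outcomes cannot be tied to the treated eye in the same way. A score built from questions about both eyes cannot be made eye-specific when it is entered in the eCRF. A single present/absent answer with no eye named does not show which eye itched or burned.

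If the untreated eye contributes, it adds the same kind of background to both arms. That creates no false difference between arms, but it can shrink a true one. In a trial that seeks to show a difference this would be conservative. Here a non-significant result can be reported as similar tolerability, so attenuation favours the conclusion that the sponsor expects.

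**Working it through.** **1. The plan's own figure, to fix n.** Inputs from section 10.1: 6 ocular AEs among 62 moxifloxacin subjects (pA = 6/62 = 0.0968), pB = 0.50, two-sided alpha 0.05. Power is not stated; 80% is assumed. With both variance terms:

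n = [pA(1 − pA) + pB(1 − pB)] × [(1.960 + 0.842)/(pA − pB)]² = (0.0874 + 0.2500) × 7.849 / 0.1626 = 16.29, so 17 per arm.

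Allowing 10% for losses gives 19 (17/0.9 = 18.9; 17 × 1.1 = 18.7). The stated 17 and 19 reproduce. The calculation concerns AE incidence and uses neither the ICO nor the symptoms, so it says nothing about power for tolerability.

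**2. ICO.** The documents give no SD for ICO change, no expected difference and no between-eye correlation. The following is an illustration under stated assumptions:

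- true difference between arms of 1.0 SD in right-eye ICO change;
- two-sample t-test, two-sided 0.05, 17 per arm (the size before allowance for losses, since the primary analysis is per protocol);
- no treatment effect in the left eye, and equal SDs in the two eyes.

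If a subject reports the mean of the two eyes, the raw difference halves to 0.5. The SD of the mean is √((1 + ρ)/2), where ρ is the between-eye correlation. The standardised effect is 0.5/√((1 + ρ)/2).

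| How subjects answer | Standardised effect | Power, 17 per arm | Power, 19 per arm |
|---|---|---|---|
| For the treated eye | 1.00 | 0.81 | 0.85 |
| Average, ρ = 0 | 0.71 | 0.52 | 0.56 |
| Average, ρ = 0.5 | 0.58 | 0.37 | 0.41 |
| Average, ρ = 0.8 | 0.53 | 0.32 | 0.35 |
| Average, ρ = 1 | 0.50 | 0.29 | 0.32 |

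**3. Symptoms.** Averaging does not apply to a present/absent answer. Suppose instead that present means present in either eye, that the eyes are independent, and that the untreated eye is symptomatic with probability u in both arms. A right-eye rate p is then recorded as 1 − (1 − p)(1 − u), and the difference between arms is multiplied by (1 − u). For assumed right-eye rates of 10% and 50%, with 19 per arm (secondary outcomes use the safety population) and Fisher's exact test:

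| u | Recorded rates | Difference | Power |
|---|---|---|---|
| 0 | 10.0% vs 50.0% | 0.40 | 0.71 |
| 5% | 14.5% vs 52.5% | 0.38 | 0.63 |
| 10% | 19.0% vs 55.0% | 0.36 | 0.55 |
| 20% | 28.0% vs 60.0% | 0.32 | 0.42 |
| 30% | 37.0% vs 65.0% | 0.28 | 0.32 |

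If the untreated eye is quiet (u = 0), nothing is lost.

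**The case against.** **The symptom questions.** A reader might infer from the words *in general* that the symptom interview covers both eyes. The text does not support this. The words are followed at once by a reference to the period since the last visit, so they most naturally describe the time window. The symptom definitions mix singular and plural, and the right-eye recording rule opens the same section 7.4.4, so a right-eye reading is available. This stands: the eye is unspecified, not bilateral. The gap remains, because nothing tells the evaluator which reading to use.

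**Dilution as a fact.** A reader might also infer that the untreated eye necessarily dilutes both outcomes. It depends on how subjects answer. The ICO intensity items ask how strong a sensation was when it was felt, so a subject with one irritated eye can answer for that eye, and nothing on the form asks for an average. Subjects are ophthalmologically healthy and use no topical eye medication, so the left eye may rarely be symptomatic. This stands too: attenuation is possible, not established.

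**A single power figure.** Quoting only the fall from 0.81 to 0.29 would present the worst case as the result. It needs both averaging and a between-eye correlation of 1.

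**The decision rule.** Reading non-significance as similarity is a separate weakness that touches every primary variable. Section 3.2 says that when the two rejection conditions are not both met, the result is absence of evidence. But the table in 10.3.1 still gives the similarity reading, so the direction of any attenuation remains relevant.

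**The published questionnaire.** Section 7.4.4.7 describes the ICO as a Rasch-based 0–100 scale. Keeping its wording is a defensible choice, and a right-eye line above items about both eyes could confuse. This stands, and it is why the ICO fix needs an alternative.

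**Conclusion.** The point holds as a mismatch in wording. Treatment and the stated unit of analysis are the right eye; the only primary tolerability outcome asks about both eyes; and the symptom questions leave the eye open. Untreated-eye complaints can enter both outcomes and can pull the arms together.

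The size cannot be established from the documents. Under the assumed 1.0 SD right-eye effect with 17 per arm, ICO power lies between 0.29 and 0.81, depending on how subjects answer and on the between-eye correlation. For symptoms, under the either-eye assumption, the difference shrinks in proportion to the untreated-eye symptom rate: from 0.40 to 0.38 at a rate of 5%, and not at all if that eye is quiet. No bias towards either product follows, since both arms are affected alike.

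This is a minor point, worth acting on because the symptom part costs almost nothing and the ICO is the sole primary tolerability measure.

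**What to change.** **Symptoms.** In section 7.4.4.3 and Table 2, ask and record each symptom as present or absent for the treated right eye. This is an interview item with no scoring scale described, so the change costs only form and protocol wording.

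**ICO.** Choose one of the following and state it in section 7.4.4.7:

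- Add an instruction to annex 16.4, used identically at the baseline and final visits, to answer for the right eye, after checking that the 0–100 Rasch scoring still applies. The downside is a departure from the source questionnaire, equal in both arms.
- Keep the published wording, state that the ICO is a both-eyes measure, and state in section 10.3.1 that a non-significant ICO difference will not be read as similar tolerability of the treated eye.

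Neither option needs extra subjects, visits or procedures.
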